### **6.8.3 Censoring**

The underlying principle is that the censoring date should be the last date a patient was known to be free of an endpoint event (e.g. free of each component of HHF + CV death).

For all endpoints except all-cause mortality and cause-specific death, patients without occurrence of a specific endpoint (composite endpoint or individual components) will be considered censored at the individual day of trial completion.

The individual day of trial completion will be the latest of:

- the last date the patient could be followed up for all non-fatal events as documented in the eCRF
- last onset of an AE or date of death
- onset dates of adjudicated events
- end of treatment
- last visit date (NYHA class, EQ-5D, KCCQ, pregnancy test, vital signs, ECG, or central laboratory- reported )

Censoring is considered independent from study drug intake.

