Vital status must be collected at the end of trial for patients that withdraw consent from trial participation, if allowed by local regulations.

Patients lost to follow-up

If a patient is lost, every effort will be made by the Investigator and site staff to contact and locate the patient before the patient is declared lost to follow-up. Investigators and site staff must use every possible allowable means, according to local regulations, to locate patients who have missed visits. Efforts to contact the patient may include but are not limited to:

- Calling all numbers for patient and listed contacts (including in the evening and on weekends).
- Calling primary care physician, referring specialist and/or other listed physicians for more recent information, date of last office visit or to determine vital status.
- Sending an email and follow up with mailing certified letters (return receipt requested) to all known patient addresses and all listed contacts (e.g., relatives, friends, neighbours) that were provided by the patient.
- Reviewing patient's records and medical notes for any details of a hospitalisation, doctor's visit or other procedure that may indicate location or status of subject.
- Use Internet to search for possible contact information for the patient.
- Try reverse directory for phone numbers to get possible addresses and/or new contact details.
- Utilise social networking sites.
- Check local, regional, and national public records to locate the patient or search for vital status in accordance with local law.
- Consider home visit.
- Contact patient finder service.

Pregnancy

If a patient becomes pregnant during the trial, the trial medication will be stopped, the patient will be followed up during the trial and until birth or termination of the pregnancy (see further details in [Section 5.3.4.2](#)).

An excessive withdrawal rate can have a severe negative impact on the scientific value of the trial. The "Intention To Treat" analysis requires that all randomised patients be followed until trial end even if the trial medication was temporarily interrupted, discontinued or never started. Every effort should be made to keep the patients in the trial as scheduled. This includes careful patient selection and appropriate explanation of the trial requirements and

procedures prior to enrolment as well as an explanation of the consequences of premature withdrawal.

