## **5. ENDPOINTS**

### **5.1 PRIMARY ENDPOINT**

The primary endpoint is the composite of time to first event of adjudicated CV death or adjudicated HHF.

For further clarification: Adjudicated CV death always includes death adjudicated as death due to undetermined cause. This is applicable throughout all analyses wherever adjudicated CV death is mentioned.

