#### Missing date of trial completion (=last contact or date of death)

If the date is completely missing the following rules will be applied:

- If a patient has withdrawn informed consent, this date will be imputed by the date of IC withdrawal.
- If a patient died and has not withdrawn consent and is not lost to follow-up, this date will be imputed by the date of death.
- If a patient did not die, the date of trial completion will be imputed by the last date the patient was known to free of non-fatal events. This is defined as the maximum of
  - the last date the patient could be followed up for all non-fatal events as documented in the eCRF
  - last onset or end date of an AE

- Onset of an adjudicated event
- End of treatment
- last visit date (NYHA class, EQ-5D, KCCQ, pregnancy test, vital signs, ECG, or central laboratory reported)

In case of a partially missing date, if the imputed date is before the first day (after the last day) of the month/year given as partial date, the first day (last day) of the month/year will be used.

All other cases need to be assessed by the trial team on an individual patient basis, using the above points as guidance.

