#### All-cause mortality

A patient, without the event will be censored at the latest of

- Individual day of trial completion (without the restrictions defined above for patients with withdrawn consent or lost to follow-up)
- Last date known alive from the vital status page

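### SAP 6.8.3 carries withdrawn, lost or vital-status-only patients as HHF-free up to a later non-CV death, and the restriction it refers to for such patients is not in that section

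*SAP*

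**What the plan says.** SAP 6.8.3 opens with a principle: "the censoring date should be the last date a patient was known to be free of an endpoint event". For every endpoint other than death endpoints, it then censors event-free patients at the individual day of trial completion, which is the latest date in a list. The list includes "the last date the patient could be followed up for all non-fatal events as documented in the eCRF" and also "last onset of an AE or date of death". It does not include a last date known alive, and it has no separate branch for patients who withdrew or were lost.

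The all-cause mortality rule in the same section adds "Last date known alive from the vital status page" and uses the completion day "without the restrictions defined above for patients with withdrawn consent or lost to follow-up". No such restrictions are written earlier in 6.8.3.

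The nearest rule is in SAP 6.6.2, for a missing date of trial completion: "If a patient has withdrawn informed consent, this date will be imputed by the date of IC withdrawal". The next item there uses the date of death only for patients who neither withdrew consent nor were lost.

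The composite rule in 6.8.3 counts an event in any component. Otherwise it censors at the earliest component date. Patients who did not complete planned treatment get no cap at treatment stop.

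Protocol 7.3.1 censors at the end of the planned treatment phase or the last day known event-free, whichever comes first. Protocol 3.3.4.1 provides for death to be known without HHF follow-up: "Vital status must be collected at the end of trial for patients that withdraw consent from trial participation", where local rules allow. Its Option 4 permits collection of vital status alone.

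**The concern.** A date of death shows that the patient was alive until then. It says nothing about whether a heart failure hospitalisation occurred after contact ended. Taking the latest of the listed dates lets the death date override the last date on which non-fatal events could be ascertained. The length of follow-up for HHF then depends on what later happened to the patient: a death extends it and survival does not.

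The unobserved interval enters as HHF-free exposure in the primary Cox model, in time to first HHF, and in the joint frailty model for recurrent HHF (SAP 7.5.1.1), which assumes independent censoring. In addition, a programmer cannot implement the mortality sentence as written, because the restrictions it lifts are not defined in the section.

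**Working it through.** **1. The rule applied.** Take a patient last followed for HHF at month 6 who did not complete planned treatment.

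| Later status | HHF time at risk | Composite |
|---|---|---|
| Non-CV death, month 24 | 24 months (24 − 6 = 18 unobserved) | censored at month 24 |
| Found alive, month 30 | 6 months | censored at month 6, the earlier component date |
| CV death, month 24 | 24 months (18 unobserved) | event at month 24 |

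Under the principle at the head of 6.8.3, and under Protocol 7.3.1, the first patient would be censored at month 6, like the second.

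**2. The plan's own figures.** For hazard ratio (HR) 0.80, 90% power and two-sided 0.05, Schoenfeld gives 4 × (1.960 + 1.282)² / (ln 0.8)² ≈ 845 events and Freedman gives 852, against the stated 841. Power with 841 events is 0.899. With exponential survival, a 15% yearly placebo risk, 18 months' accrual and 20 months' follow-up, N is 2,843 against 2,850. None of these uses the censoring rule, so none changes.

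**3. Size of the effect.**
- From the documents: 1:1 allocation, about 3,600 patients planned (SAP 9.6), drop-out below 1% per year, 18 + 20 months.
- Assumed, per 100 patient-years: placebo HHF 10, CV death 5, non-CV death 3; empagliflozin 8, 4 and 3. Hazards are constant and every death after loss becomes known.

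Write h, v and m for the hazards of HHF, CV death and any death, l for loss, and c for time to trial end (20 to 38 months, mean 2.417 years).

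Patients lost: l/(l + m) × [1 − exp(−(l + m)c)]. At l = 0.01 and mean c:
- placebo 0.01/0.09 × (1 − e^(−0.2175)) = 0.0217
- empagliflozin 0.01/0.08 × (1 − e^(−0.1933)) = 0.0220
- 1,800 × (0.0217 + 0.0220) ≈ 79, or about 78 when averaged over c.

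Lost with no prior HHF and then dying before trial end: D = ∫ l·exp(−(l + m + h)t)·[1 − exp(−m(c − t))] dt. This gives 6.6 patients across 3,600. About 3.9 are CV deaths, which leaves 6.6 − 3.9 = 2.7 non-CV deaths.

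Simulation with 3 million patients per arm, comparing censoring of every lost patient at last contact with literal 6.8.3:

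| Loss per year (placebo / empagliflozin) | Composite HR | HHF HR |
|---|---|---|
| 1% / 1% | 0.7976 → 0.7978 | 0.7967 → 0.7968 |
| 5% / 5% | 0.7993 → 0.7998 | 0.7991 → 0.7996 |
| 1% / 2% | 0.7982 → 0.8011 | 0.7975 → 0.7969 |
| 2% / 1% | 0.8001 → 0.7975 | 0.8018 → 0.8026 |

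At 1% in both arms, the placebo composite rate goes from 15.01 to 15.06 per 100 patient-years and the placebo HHF rate from 10.01 to 10.00.

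**4. Which deaths drive the 0.003.** Let T be the observed event-free time and U the time from loss to death among the D patients. The composite rate is:
- last contact: h + v
- literal: [(h + v)T + D·v/m] / (T + U)
- CV deaths counted, non-CV deaths censored at last contact: [(h + v)T + D·v/m] / (T + U·v/m)

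Evaluated at 1% versus 2% loss, the composite HRs are 0.8000, 0.8028 and 0.8031. The shift therefore comes from counting CV deaths after loss, not from the non-CV time.

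**The case against.** The strongest reply is that the intent is clear. The 6.6.2 item on deaths states the restriction for both withdrawn and lost patients and comes before the back-reference in 6.8.3. The opening principle and Protocol 7.3.1 agree with it, and Protocol 3.3.4.1 ends the trial for a patient who withdraws consent. This stands as evidence of intent. But 6.6.2 governs only missing completion dates, and the list in 6.8.3 does not cite it, so it does not supply the rule.

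Existing analyses also help. SAP 7.4.2 has an imputation for patients lost without a primary event, a treated-set analysis limited to 30 days after stopping, and a Kaplan-Meier display of time to censoring. SAP section 7 counts patients lost for vital status and for the primary endpoint. These would expose much of a problem. They do not correct the primary rule, and if the completion day is itself the death date, it is unclear whether the gap before a non-CV death would be imputed.

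Stronger readings are tempting, and the documents do not support them:
- *The primary result is materially biased.* Under the stated drop-out assumption the shift is in the third or fourth decimal place.
- *All deaths after loss could add primary events in one arm.* Non-CV deaths add none, and nothing in the plan points to loss on one side only.
- *Survivors of the same loss contribute nothing.* They contribute all their time up to last contact.
- *A poorly documented death after withdrawal would become a primary event.* SAP 5.1 says "Adjudicated CV death always includes death adjudicated as death due to undetermined cause", but when that verdict is given depends on the event committee's charter, which is not among these documents.
- *The restriction is missing from the whole SAP.* It is missing from 6.8.3. A related form exists in 6.6.2.

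**Conclusion.** The point holds as a defect in a stated rule. The literal list in 6.8.3 contradicts the section's own principle and Protocol 7.3.1, and its back-reference has no target in the section. It is minor. With 1% loss per year in both arms, roughly 7 of 3,600 patients are involved, about 3 of them non-CV deaths. The hazard ratio changes by less than 0.001 with equal loss up to 5% per year, and by about 0.003 for the composite with 1% versus 2% loss, against the arm with more loss. Power and the 841 events are unaffected.

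These sizes rest on the assumed split of the 15% rate into HHF and CV death, the assumed non-CV death rate, constant hazards, and complete knowledge of deaths after loss. The effect grows with the loss rate and with imbalance between arms.

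**What to change.** - In SAP 6.8.3, extend the 6.6.2 restriction. For endpoints with a non-fatal component, patients without an event who withdrew, were lost or gave vital status only are censored at the last date they were followed for all non-fatal events, whether or not a later non-CV death is known. Make this date override the whole list, since the onset of a fatal adverse event or of an adjudicated event would otherwise extend follow-up in the same way.
- State explicitly that CV deaths found after that date count in the primary composite, and add one sensitivity run that excludes them. Counting them suits the intention-to-treat aim, but it leaves the composite shift under unequal loss in place. The run is there to show its size.
- Keep all deaths in the CV-death and all-cause mortality analyses.
- Align SAP 6.6.2, SAP 6.8.3 and Protocol 7.3.1, and say how the date applies in the joint frailty model, whose likelihood uses one follow-up time for both processes.

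The cost is a sentence or two, one derivation and one extra run. A handful of patients have slightly shorter time at risk.

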#### All-cause mortality

A patient, without the event will be censored at the latest of

- Individual day of trial completion (without the restrictions defined above for patients with withdrawn consent or lost to follow-up)
- Last date known alive from the vital status page

#### Endpoints of any cause-specific death, e.g. CV death

The same censoring rule as in all-cause mortality applies, and in addition, date of death if died from other causes than the one specified in the endpoint.

#### Endpoints based on laboratory data only

Patients who already fulfil the respective condition at baseline are not considered in the number of patients at risk for this endpoint.

If a baseline laboratory measurement is not available for the parameter of interest, it is assumed that the patient did not experience the condition corresponding to the endpoint at baseline and the patient is included in the patients at risk for this endpoint. Patients without an event and available post-baseline laboratory measurements will be considered censored at the date of last laboratory sampling of the corresponding parameter. Patients with missing baseline laboratory required to derive a change from baseline and patients without laboratory data following the baseline measurement will be censored on the date of randomisation.

#### Composite endpoints

Only patients that are included in the analyses for all components of the composite endpoint will be included in the analysis of the composite.

Of those, a patient with at least one event in any of the components of the composite will be considered to have an event and the date of the first event will be used for the composite

endpoint. A patient without an event will be considered censored at the earliest of all censoring dates of the component endpoints.

For efficacy endpoint analyses (endpoints described in [Sections 7.4-7.6](#)):

As described in [Section 4](#), for patients that completed the treatment phase as planned (primary reason for end of treatment being completion of treatment period according to protocol) the follow-up period will not be included in the time at risk for efficacy endpoints. Therefore for those patients, the minimum of the treatment discontinuation date and the above described dates will be used for censoring, except if specifically noted otherwise (for the sensitivity analysis). For patients that did not complete the treatment phase, the dates defined above will be used.

For the primary endpoint and the key secondary endpoint of recurrent HHF, additionally there will be a sensitivity analysis considering all events up to individual trial completion including the FU period.

Censoring for analyses up to trt stop + x days

For any analyses until a certain number of x days after treatment discontinuation (e.g. sensitivity analyses until 30 days after treatment discontinuation), censoring time will be the minimum of the censoring time as described above and treatment discontinuation + x days. Patients with an event after treatment discontinuation + x days will be censored at treatment discontinuation + x days.

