3.3.4 Removal of patients from therapy or assessments

3.3.4.1 Removal of individual patients

This is a long-term outcome trial and every effort should be made by the site staff to encourage patients to remain in the trial and on trial medication unless medical condition substantially changes to alter the safety profile. If a patient is withdrawn from the trial the ExSC and the Sponsor should be informed immediately about each individual case.

Prematurely discontinuation of trial medication

For patients who prematurely discontinue trial medication all efforts should be made to observe these patients and ask them to continue to attend the scheduled visits until the end of trial. It is expected that all efforts are made to follow up on the collection of all adverse events, outcome events and concomitant therapy, and to have a complete dataset without missing data.

If a patient who prematurely discontinued trial medication is not willing to return to the predefined trial visits, at minimum a telephone call every 24 weeks (preferably every 12 weeks) and a telephone call at trial end will be required, to document the occurrence of

outcome events and vital status. If possible, other AE's and concomitant therapy changes since last visit must be recorded.

Every attempt must be made by the investigator to ensure patients continue participating in the trial during trial medication interruptions and after discontinuation of trial medication. Patients who prematurely discontinue trial medication are allowed to restart treatment, at any time if appropriate in the opinion of the Investigator. At every visit following trial medication discontinuation Investigators must consider if trial medication can be re-started.

Patients that are not actively taking trial medication may be less motivated to adhere to the scheduled trial visits. Investigators and site staff should work to detect early signs of losing interest and readily present such patients (not actively taking trial medication) with the following options to encourage continued participation:

- Option 1 Continue to attend regularly scheduled trial visits at the centre until the trial ends
- Option 2 Conduct all remaining trial visits over the phone

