### **6.8.2 Date of event**

For adjudicated events, the date determined by the adjudication committee will be used; this can be different from the investigator reported date.

For the endpoints of time to CV death, time to all-cause mortality and time to non CV death the respective death date will be used rather than time to the first onset of the fatal AE.

For composite outcomes, e.g. time to adjudicated HHF or adjudicated CV death, the earliest onset date of the corresponding components will be used. For the component of CV death or other death components, date of death will always be used rather than the onset date also for composite outcomes.

For endpoints, where myocardial infarction (MI) and stroke are included as a fatal and non-fatal component, the onset of the event is considered for the derivation of time to first occurrence, not the date of death. For time to CV death the date of death is used for a fatal MI or fatal stroke.

The time to first occurrence type of endpoints based on laboratory data including endpoints including the requirement a “sustained” measurement are determined by the date of the first measurement that fulfils this condition.

For events with multiple possible episodes, such as HHF or all-cause hospitalisation, the onset date of the first episode will be used unless noted otherwise. The same applies to time-to-AE analysis.

For efficacy endpoint analyses (endpoints described in [Sections 7.4-7.6](#)):

As described in [Section 4](#), the follow-up period will not be included in the time at risk for efficacy endpoints. Therefore events later than the date of treatment discontinuation (if reason for discontinuation was completion) will not be counted.

For the primary endpoint and the key secondary endpoint of recurrent HHF, additionally there will be sensitivity analysis including all events up to individual trial completion including the FU period.

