## **7.6 FURTHER ENDPOINTS**

### Time to event endpoints

Further time to event endpoints will generally be analysed in a Cox proportional hazards model similar to the primary analysis on RS. If the endpoint does not include any cause of death, a CIF plot with all-cause mortality as competing risk will be displayed; otherwise, a CIF plot with causes of death not included in the endpoint as competing risk will be displayed.

If there are less than 14 patients with events, then only descriptive statistics will be presented.

Further time to event endpoints are the following:

- Time from first to second adjudicated HHF
- Time to first all-cause hospitalisation
- Time to new onset of atrial fibrillation
- Time to adjudicated MI (fatal or non-fatal)
- Time to adjudicated stroke (fatal or non-fatal)
- Time to adjudicated TIA
- Time to first event of all-cause mortality or all cause hospitalisation
- Time to first event of adjudicated CV death or adjudicated non-fatal MI
- Time to first event of adjudicated CV death or adjudicated non-fatal stroke
- Time to first event of adjudicated CV death, adjudicated non-fatal MI or adjudicated non-fatal stroke (3-point MACE)
- Time to progression to macro albuminuria (defined as UACR >300 mg/g) from baseline for patients with baseline UACR ≤ 300 mg/g

- Time to first new onset of sustained normo- or micro albuminuria (UACR  $\leq$  300 mg/g) in patients with macro albuminuria at baseline
- Time to first new onset of sustained normo albuminuria (UACR  $<$  30 mg/g) in patients with micro- or macro albuminuria at baseline
- Time to first event of composite renal endpoint or adjudicated CV death
- Time to first event of composite renal endpoint, adjudicated CV death or adjudicated HHF
- Time to first event of composite renal endpoint or all-cause mortality
- Time to achievement of NT-proBNP  $<$  1000 pg/mL
- Time to first acute kidney injury (based on the preferred term)
- Time to non-cardiovascular (non-CV) death (death cases not included in the definition of adjudicated CV death)
- Time to first investigator defined CV hospitalization

Composite renal endpoint defined as: *chronic dialysis or renal transplant or sustained\* reduction of  $\geq$ 40% eGFR (CKD-EPI)cr or*

- *(for patients with eGFR (CKD-EPI)cr  $\geq$ 30 mL/min/1.73 m^2 at baseline): sustained eGFR  $<$ 15 mL/min/1.73m^2*

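### SAP 6.8.3: in composites with a laboratory component, patients with and without an event have different ends of follow-up, so time at risk depends on outcome

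*SAP*

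**What the plan says.** **Events.** Under Composite endpoints in SAP 6.8.3, "a patient with at least one event in any of the components of the composite will be considered to have an event", dated at the first such event.

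**Censoring.** In the same paragraph, "A patient without an event will be considered censored at the earliest of all censoring dates of the component endpoints".

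**Laboratory components.** Event-free patients with post-baseline samples "will be considered censored at the date of last laboratory sampling of the corresponding parameter", while "patients without laboratory data following the baseline measurement will be censored on the date of randomisation".

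**Who is covered.** For planned completers, SAP 6.8.2 applies one limit to events as well: "Therefore events later than the date of treatment discontinuation (if reason for discontinuation was completion) will not be counted". For the others, SAP 6.8.3 says: "For patients that did not complete the treatment phase, the dates defined above will be used". No section limits their component events to the last sample.

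**Competing text.** The opening of SAP 6.8.3 censors event-free patients at individual trial completion and names composites in that rule.

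**Follow-up after stopping drug.** One option in Protocol 3.3.4.1 is "Conduct all remaining trial visits over the phone". Others collect outcomes or vital status only at trial end. The Flow Chart schedules no eGFR at telephone visits.

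**Endpoints.** SAP 7.6 lists three endpoints of the form "Time to first event of composite renal endpoint" combined with CV death, with CV death or HHF, and with all-cause mortality. SAP 7.5.2 has the renal composite itself (dialysis, transplant or sustained eGFR criteria).

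**The concern.** Censoring must not depend on what happens to the patient later. Here it does. Once sampling has stopped but outcome follow-up goes on, the only patients left in the risk set are those who will later have an event. Those who stay event-free are removed retrospectively at their last sample.

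This raises the incidence rate in any arm where it happens. If loss of sampling differs between arms, it also moves the hazard ratio in favour of the arm with less loss. Because the opening of 6.8.3 and its composite paragraph give different dates, two programmers could also derive different datasets from the same SAP.

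**Working it through.** **1. The plan's own figure.** The documents give no figure for these composites. Their design figure for the primary endpoint reproduces: events = 4(1.960 + 1.282)² / (ln 0.80)² = 42.03 / 0.0498 ≈ 845, against 841 planned. With 18 months of uniform accrual, 20 months of further follow-up and hazard −ln(0.85), 2850 patients give 843 events. The calculations in steps 3 and 4 use this accrual and follow-up with 1425 per arm, except where stated.

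**2. The rule applied to one patient.** Suppose a patient stops drug, has the last sample at month 3 and is followed by telephone to month 24.

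| | Event-free | Dies at month 20 |
|---|---|---|
| Last sample at month 3 | 3 months, no event | 20 months, event |
| No post-baseline sample | 1 day, no event | 20 months, event |

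The one day follows from SAP 6.8: censoring date − start date + 1.

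**3. Effect on incidence.** Assumptions not in the documents: composite hazard 0.15 or 0.08 per year; sampling ends at 2%, 5% or 10% per year while outcome follow-up continues; hazard unchanged afterwards.

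Placebo arm, hazard 0.15, loss 5% per year:
- About 9.5% of patients lose sampling before an event. They have 24 events in 160 patient-years after the last sample, but the rule keeps only 20 of those years.
- The rate in that window is 24/20 = 120 per 100 patient-years, against 24/160 = 15.
- Whole arm: 431 events at 15.01 per 100 is about 2871 patient-years. Removing 160 − 20 = 140 leaves 2731, and 431/2731 = 15.78 per 100.

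| Laboratory loss per year | Hazard 0.15: SAP rule / full follow-up | Hazard 0.08: SAP rule / full follow-up |
|---|---|---|
| 2% | 15.28 / 14.98 (+2%) | 8.18 / 8.00 (+2%) |
| 5% | 15.78 / 15.01 (+5%) | 8.44 / 7.99 (+6%) |
| 10% | 16.57 / 15.02 (+10%) | 8.89 / 7.98 (+11%) |

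The inflation is roughly one percentage point for each 1% per year of loss. If 13% per year stop drug and 30% of them are unsampled, loss is 0.13 × 0.30 = 3.9% per year. At 18% and 60% it is 0.18 × 0.60 = 10.8%. This gives the 4–11% range.

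**4. Effect on the hazard ratio (true value 1, hazard 0.15).** The same simulated data give 0.994 under full follow-up, so that is the comparator.

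| Loss per year, placebo / active | SAP rule | Ratio to 0.994 |
|---|---|---|
| 5% / 5% | 0.994 | 1.00 |
| 6% / 4% | 0.974 | 0.98 |
| 10% / 5% | 0.945 | 0.95 |
| 4% / 6% | 1.014 | 1.02 |

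A second simulation used 3,600 patients, an assumed total duration of 30 months, stopping at 18% against 13% per year and 60% of stoppers unsampled. It gave 0.981 under the SAP rule against 1.000. With 30% unsampled it gave 0.993 against 1.003. At about 913 events the standard error of the log hazard ratio is 2/√913 = 0.066, so a shift of ln 0.981 = −0.019 is about 0.3 standard errors.

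**5. Testing repairs on the visit schedule.** On-site samples fall at weeks 4, 12, 32 and 52 and then every 24 weeks, so a patient's last sample precedes death. Cutting events at the last sample kept fewer than 1% of deaths in the composite. With assumed hazards of 0.07 (death) and 0.03 (laboratory), 18% per year stopping and 30–60% of stoppers unsampled, the true rate is 0.100. The SAP rule gave 0.104–0.108. Keeping all events and censoring at the end of clinical follow-up gave 0.096–0.098. With no laboratory loss, the SAP rule and full follow-up gave identical rates.

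**The case against.** **The general rule cures it.** If composites are censored at individual trial completion, as the opening of 6.8.3 says, there is no asymmetry. But the later paragraph is specific to composites and gives another date, and nothing says which prevails. The stated aim of censoring at the last date known free of each component does not restrict which events count.

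**The population is small.** The Protocol works against laboratory loss. Stoppers have an end-of-treatment visit and a 30-day follow-up visit, both with eGFR, and should then keep scheduled visits. Telephone follow-up is for those unwilling to attend, and the one-day survivor should be rare. This stands: the size is unknown, and every stopping and sampling rate used here is assumed.

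**The effect is small and exploratory.** This also stands. All four endpoints are outside the confirmatory hierarchy. The 0.15 hazard suits only the composite with HHF. In the secondary renal composite only dialysis and transplant are non-laboratory, so its effect is smaller, and it was not quantified.

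**Stronger readings a reader might infer.**
- That the result is biased towards empagliflozin: the documents give no stopping or sampling rates by arm, and the shift can go either way.
- That the primary result is affected: CV death and HHF have no laboratory component.
- That late events carry no time at risk: those patients contribute time up to the event. What is lost is the time of those who remain event-free.

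**Conclusion.** The point holds as a defect in the censoring rule for composites that mix laboratory and clinical components. It follows from the SAP's wording and needs no assumption. Its size does. With 13–18% per year stopping and 30–60% of stoppers unsampled, incidence is about 4–11% above what the same events give over full clinical follow-up. The hazard ratio is unbiased if laboratory loss is equal between arms and moves by a few percent if it is not, for example to 0.98 under the null.

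The change is worth making because the correction is cheap and two parts of one section conflict. It does not touch the primary endpoint, recurrent HHF, the eGFR slope, the 841 events or alpha.

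**What to change.** In SAP 6.8.3, for composites that combine laboratory and clinical components:

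1. Keep every component event at its own date. Censor event-free patients at the end of clinical outcome follow-up, which for planned completers is the treatment discontinuation date. This agrees with the opening of 6.8.3.
2. Delete the earliest-date rule for these composites, or limit it to composites where it is needed, so that one rule applies.
3. Add a sensitivity analysis that ends both events and time at risk at one date per patient, such as the last sample plus the scheduled sampling interval.
4. Tabulate by arm the patients whose outcome follow-up outlasts laboratory sampling, with the length of the gap.

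Do not restore symmetry by cutting events at the last sample: that would remove almost every death, including deaths in patients who attended all visits.

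Cost: one SAP paragraph, one changed derivation, one additional derivation for the sensitivity analysis and one table. The drawback is that laboratory events in unsampled stoppers are slightly under-counted (0.096–0.098 against a true 0.100 in step 5), which the sensitivity analysis helps to gauge.
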